6.4 Outcome variables

6.4.1 Security variables

6.4.1.1 Primary outcome variables

- Presence of adverse events.
- Intraocular pressure.
- Visual ability
- Laboratory tests: BHc, QS and PFH.
- Ocular surface staining with fluorescein and lissamine green using the Oxford scale.
- Ophthalmological signs: conjunctival hyperemia, chemosis.

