6.4.3 Methods and scales to be used for the measurement of the variables

Variable	Unity	Symbol	Type	Measuring method	Normal value
Age	Years	--	Continuous	Calculation from the date of birth	NA
Gender	Female/ Male	F / M	Nominal	Direct questioning	NA
Adverse events	Number of cases	n	Discreet	Count	NA
Intraocular pressure	Milimeters of mercury	mmHg	Continuous	Goldman's applanation tonometry	11 - 21
Visual ability	Fraction	Snellen	Nominal	Primer	
Tear rupture time	Seconds	s	Continuous	Direct count	> 10
Eye comfort index	points	--	Discreet	Questionnaire	
	Present / Absent	--	Nominal	Comprehensive valuation	Absent
Vital signs					
Heart rate	Beats per minute	lpm	Discreet	Auscultation	60 – 100
Breathing frequency	Breaths per minute	rpm	Discreet	Auscultation	12 – 24
Systemic blood pressure	Milimeters of mercury	mmHg	Continuous	Non-invasive auscultatory measurement	< 120 / 80
Previous segment					
Ocular surface staining	Degrees	--	Discreet	Direct observation with fluorescein and green lysamin stain	Oxford Scale
Ophthalmologic signs and symptoms					

Variable	Unity	Symbol	Type	Measuring method	Normal value
Conjunctival hyperemia	Normal / Very Light / Mild / Moderate / Severe	--	Ordinal	Direct observation. Classification of Efron.	Normal
Chemosis	Present / Away	--	Nominal	Direct observation	Absent
Burning	Severity: Absent, very mild, mild, moderate and severe	--	Nominal	Direct questioning	Absent
Foreign body sensation	Severity: Absent, very mild, mild, moderate and severe	--	Nominal	Direct questioning	Absent
Pruritus	Frequency: At all times, almost at all times, 50% of the time, almost in no time, at any time	--	Nominal	Direct questioning	Absent
Posterior segment					
Macula	Normal / Abnormal	--	Nominal	Direct observation	Normal
Optical disk integrity	Normal / Abnormal	--	Nominal	Direct observation	Normal
Blood count					
Erythrocytes		M/uL	Continuous		
Hemoglobin	Grams over deciliter	g/dL	Continuous		
Hematocrit	Percentage	%	Continuous		
VGM	Femto liters	fL	Continuous		

Variable	Unity	Symbol	Type	Measuring method	Normal value
HCM	picograms	pg	Continuous		
CMHbG	Grams over deciliter	g/dL	Continuous		
Leukocytes	Thousands per liter units	Mil/uL	Continuous		
Platelets	Thousands per liter units	Mil/uL	Continuous		
Myelocytes	Percentage	%	Discreet		
Metamyelocytes	Percentage	%	Discreet		
Bands	Percentage	%	Discreet		
Segmented	Percentage	%	Discreet		
Lymphocytes	Percentage	%	Discreet		
Monocytes	Percentage	%	Discreet		
Eosinophils	Percentage	%	Discreet		

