Basophils	Percentage	%	Discreet		
Blastos	Percentage	%	Discreet		
Blood chemistry					
Glucose	Milligrams on deciliter	mg/dL	Continuous		
Urea	Milligrams on deciliter	mg/dL	Continuous		
Creatinine	Milligrams on deciliter	mg/dL	Continuous		
Liver function tests					
Alanine transferase	Units on liter	U/L	Continuous		
Aspartate transferase	Units on liter	U/L	Continuous		
Total bilirubin	Milligrams on deciliter	mg/dL	Continuous		
Direct bilirubin	Milligrams on deciliter	mg/dL	Continuous		
Indirect Bilirubin	Milligrams on deciliter	mg/dL	Continuous		

Table 6. Scales to be used

The following describes the methods and scales that will be used for the measurement of the variables, which are in strict alphabetical order:

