6.6.1 Calculation of the sample size

Although there are no references on the calculation of sample size in phase I studies, it was considered pertinent to perform it according to the presentation of adverse events reported by Schwab IR, et al, in a case-control study in 423 subjects with ophthalmic solutions of levofloxacin 0.5 % and ofloxacin 0.3% for 5 days. [22]

The percentage of adverse events that occurred with the preservative-free HS solution was 7.3%, which is why we consider that at least more than 60% of the exposed subjects will not present this rate of adverse events.

The sample size was calculated using the formula for proportions

$$n = \left[(p_1)(p_2) + (p_1)(p_2) \left(\frac{Z_{1-\alpha}}{2} + Z_{1-\beta} \right)^2 \right] / (p_1 - p_2)^2$$

With a statistical confidence of 95% corresponding to the type I error, equal to 1.96, with a power of 80%, corresponding to the type II error, equal 0.84.

According to the previous calculation, the result is 12.5 subjects (13) per group. The total when considering 2 intervention groups is 26 subjects, which was increased by 20% for the probable losses. The total sample size required is 30 subjects. Therefore, each group will consist of 15 subjects, who will provide both eyes for the analysis, so that the total sample to be analyzed will be composed of 60 eyes.

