8.3 Statistical methodology

8.3.1 Analysis of primary and secondary outcome variables.

The statistical analysis will be carried out by personnel from Sophia Laboratories, S.A. of C.V The statistical program SPSS version 19 (IBM Corporation, Armonk, NY, USA) will be used.

The designated personnel will be blinded to the intervention groups. The coding will be done using consecutive numbers for each intervention group.

The data will be collected and sorted in an excel sheet. Later they will be exported to the platform of the SPSS program. The variables will be categorized according to their nature.

The result of the continuous quantitative variables will be presented in measures of central tendency: media, standard deviation and ranges. **See Table 6.** Scales to be used

The normal distribution of the results will be obtained by the Kolmogorov-Smirnov test.

The statistical analysis of the continuous **quantitative variables** to find significant differences (p) will be the following:

- Intra-group analysis: Wilcoxon rank test.
- Inter-group analysis: Mann-Whitney U test.

The level of difference to consider significance will be of an alpha of 0.05 or less.

The result of nominal and ordinal qualitative variables will be presented in frequencies, proportions and percentages. See table 1 (section 6.4.3).

The statistical analysis to identify significant differences of the **qualitative variables** will be done by creating 2x2 contingency tables and will be done as follows:

- Intra-group difference: McNemar test.
- Difference between groups: test χ^2 (Chi-square) of Pearson.

The level of difference to consider significance will be of an alpha of 0.05 or less.

For the reporting of adverse events all eyes of those participants who were randomly assigned to an intervention group after the baseline visit will be considered. The results will be expressed in number of cases (eyes).

The final report of the results will be shown in tables or graphs, as appropriate.

It will be considered that the investigational drug is safe and tolerable when there are no clinical and statistical differences in all the variables of primary outcome, with respect to its comparators.

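### The safe-and-tolerable rule spans up to 36 unadjusted comparisons, 25 of them laboratory analytes; identical products would more often than not show a nominal difference, and the plan does not say whether that alone fails PRO-174

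*Combined protocol and SAP*

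**What the plan says.** Section 8.3.1 gives the trial's only success criterion: the product is "safe and tolerable when there are no clinical and statistical differences in all the variables of primary outcome, with respect to its comparators". For each test, "The level of difference to consider significance will be of an alpha of 0.05 or less". Quantitative variables are compared by "Inter-group analysis: Mann-Whitney U test", qualitative ones by Pearson chi-square on 2x2 tables.

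Section 6.4.1.1 lists "Laboratory tests: BHc, QS and PFH" as one primary safety item. Table 6 in section 6.4.3 breaks it into separate rows, from erythrocytes through items such as "Metamyelocytes" to "Indirect Bilirubin".

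No multiplicity adjustment, hierarchy or summary laboratory endpoint appears in 8.3.1, and 8.3.2 plans nothing further. No size of between-group difference is defined as clinical for any variable. Section 6.4.3.11 lets the investigator's clinical criterion prevail on whether a laboratory result is normal, which concerns individual results and not a difference between arms.

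**The concern.** The verdict depends on every primary variable, each with its own 5% chance of a false difference, and one item on the list hides 25 tests. The more variables the rule spans, the more likely that two identical products differ somewhere by chance.

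If a statistical difference alone is enough to fail, PRO-174 could be failed by a chance blood-count result. If a clinical difference is also needed, someone must decide after seeing the data whether a chance result counts, with no limit to decide by. Under both readings the p-value is the only part of the rule that the plan makes operational. The consequence is not trivial: section 5.4 says these safety results are to support later efficacy studies and regulatory procedures.

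**Working it through.** **Plan's own figure.** The documents state no overall false-difference rate, so there is none to reproduce. Section 6.6.1 sets the error rates for a single comparison of proportions: "With a statistical confidence of 95% corresponding to the type I error, equal to 1.96". Its planned power is 80% (z = 0.84). The value 1.96 means two-sided 0.05. Group size is 15 subjects (30 eyes) per arm (section 6.6).

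**Count of comparisons, one time point each.**
- Blood count: 8 indices and cell counts plus 9 differential items = 17.
- Chemistry: 3. Liver tests: 5. Laboratory total: 17 + 3 + 5 = 25.
- Other primary safety items (6.4.1.1): adverse events, intraocular pressure, visual ability, two stains, hyperemia, chemosis = 7.
- Tolerability (6.4.1.2 and the Summary): burning, foreign body sensation, itching, comfort index = 4.
- Total: 25 + 7 + 4 = 36.

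There is a narrower reading. Section 8.3.1 assigns the Mann-Whitney test to continuous quantitative variables, and Table 6 types 13 of the 36 as discrete (nine differential items, two stains, comfort index, adverse events). That leaves 36 − 13 = 23 comparisons, of which 25 − 9 = 16 are laboratory. The Summary assigns the test to quantitative variables generally, which supports 36.

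**Independent tests.** Chance of at least one p ≤ 0.05 with no true difference = 1 − 0.95^k.

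| k | Reading | Chance |
|---|---|---|
| 16 | laboratory, narrower | 56% |
| 23 | all primary, narrower | 69% |
| 25 | laboratory | 72% |
| 36 | all primary | 84% |

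The chance passes 50% at k = 14 (51%; 49% at k = 13).

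**Correlation (assumed; the documents give none).** With the same correlation between all test statistics:

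| Correlation | 25 tests | 36 tests |
|---|---|---|
| 0.1 | 70% | 82% |
| 0.3 | 61% | 72% |
| 0.5 | 47% | 55% |
| 0.7 | 32% | 36% |

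Simulated Mann-Whitney tests at 15 per arm gave, for 36 variables, 74% to 79% at correlation 0.2 and 62% to 65% at 0.4.

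**Linked and sparse items.** Hemoglobin, hematocrit and erythrocytes move together, as do the differential percentages, the three bilirubins, and ALT with AST. Myelocytes, metamyelocytes and blasts should be near zero in healthy subjects. A simulation with an assumed healthy-subject structure of this kind gave about 57% for the laboratory tests at 15 per arm, with about 1.0 false difference expected. Adding the other 11 variables at assumed rates, one value per subject, gave about 73%.

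**Rare yes/no items fall short of 5%.** With 15 per arm and a true adverse-event rate of 7.3% in both (the rate quoted in 6.6.1), Pearson chi-square rejects 1.3% of the time.

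**Eyes as units works the other way.** Section 6.6.1 analyses 60 eyes. If eyes are treated as independent, one test at nominal 0.05 has true error 2 × P(Z > 1.96/√(1 + ρ)), where ρ is the between-eye correlation: 11% at ρ = 0.5 and 16% at ρ = 0.95. The ranges used here are for subject-level tests.

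**The case against.** **The rule names clinical as well as statistical differences.** A reader might infer that any chance p ≤ 0.05 disqualifies PRO-174. The documents do not support that. If both conditions are needed, a nominal difference between two groups who all entered within the reference range plus a 10% margin (6.2.1) need not fail the product. This stands as a limit on the conclusion. It does not rescue the rule, because the plan neither says that both are needed nor defines a clinical difference.

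**The highest percentages are upper readings.** A reader might take 84% as the false-difference rate, or 90% (1 − 0.95^45) by adding the nine primary variables also measured at Visit 1. The first assumes 36 independent tests that each reach a full 5%, which linked analytes and sparse items rule out. The second assumes a Visit 1 comparison that 8.3.1 does not specify. This objection stands.

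**The trial is exploratory.** Section 5.6 says so, and the specific objectives in 5.5.2 are all to describe. That lowers the stakes, but 8.3.1 still attaches a yes/no verdict to the tests.

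**A false alarm is the cautious error in a safety study.** This is a strong point, and it bears on the remedy. A reader might infer that a Holm adjustment over the remaining 11 variables would repair the rule and hold the error at 5%. Under eye-level analysis it would not hold 5%, for the reason shown in the working. It also makes a verdict of safe easier to reach. With adverse-event rates of 7.3% versus 40% (the latter illustrative) and 15 per arm, chi-square power falls from 61% at 0.05 to 17% at the first Holm step, 0.05/11 = 0.0045.

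**Conclusion.** The concern holds in limited form. The rule requires no differences across as many as 36 primary comparisons at an unadjusted 0.05, and 25 of those come from one listed item. For identical products the chance of at least one nominally significant difference is about 55% to 72% for the laboratory tests alone and about 60% to 84% over all primary comparisons.

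The lower ends rest on assumed correlations and on how many items are tested; the upper ends are the independent case. With a uniform correlation of 0.5 the figures are 47% and 55%, so for the laboratory tests alone the statement that a difference is more likely than not fails from about that point.

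What the documents do not settle is whether such a difference, by itself, fails PRO-174. The count and the 0.05 level are certain; how often the product would actually be failed cannot be computed from this plan.

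**What to change.** In section 8.3.1:

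1. Remove the 25 laboratory analytes from the p-value part of the rule. Report, per arm, the number of subjects who move outside the entry limits of 6.2.1 (reference range with 10% margin).
2. For each of the remaining 11 primary variables, name one subject-level between-group comparison and report the estimated difference with its 95% confidence interval.
3. State in advance how clinical and statistical combine in the verdict, including what the sponsor will count as a clinical difference, and label all other p-values descriptive.

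Do not add Holm or a similar adjustment.

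Step 1 alone takes the independent-test figure from 84% to 1 − 0.95^11 = 43%. The 11 variables at the assumed rates gave about 38% in simulation. Because that residual is still large, steps 2 and 3 are needed as well.

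The cost is wording only; no new data are collected. The downside is that a laboratory difference no longer decides the verdict through a p-value and must be judged from the reported shifts.

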8.3.2 Additional analyzes

No additional analyzes are contemplated to those previously described. Nevertheless, these may be performed in the event that during the conduction of the study it is required to analyze specific safety aspects of any intervention, maintaining the blinding until the end of the study..

8.3.3 Population analysis and management of missing data

An intention-to-treat analysis will be carried out, where the data of the participants who have completed the final visit will be included.

9. Methods Monitoring

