6.2.3 Elimination criteria

- Withdrawal of the consent letter under information.
- Presentation of a serious adverse event.
- No tolerability or hypersensitivity to any of the compounds used during the tests (fluorescein, green lysine, tetracaine)
- No tolerability or hypersensitivity to any of the investigational drugs.
- Adherence <50% determined by the diary of the subject, of the established dose of the pharmacological intervention in any of the visits.

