6.3.2.2 Procedure to determine adherence

The final adhesion will be determined by the sponsor by means of the weight of the bottle.

Before delivering the medication to the research center, the weighing of the bottles to be delivered must be carried out. After the return of the medication by the center will be weighing. The weighing will be carried out according to the procedures regulated by the sponsor.

The adhesion will be calculated considering: the weight of the empty bottle, the weight of the drop, the weight of the bottle with the content, the calculation of the total of drops to be applied during the entire time of intervention and the total weight of the drops applied. The following simplified formula will be used:

$$Ad = \frac{(P_i - P_f)100}{P_T}$$

Where:

Ad = adhesion

P_i = weight of the bottle delivered to the subject at the start

P_f = weight of the bottle returned by the subject

P_T = weight of the posology indicated for the intervention.

$$P_T = (P_g)G$$

Where:

P_g = weight of the drop of the intervention, determined by the department of research and development

G = number of drops indicated for the intervention.

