5. TRL
6. Vital signs.
7. Evaluation of adverse events.

Final visit/ Day 8.

If the visit can not be made on the 8th, it can be done within a period of up to two days, that is, on the 9th or 10th day. Not before, since the application of the medication will not be completed as dictated the protocol.

1. Visual ability
2. Intraocular pressure.
3. Eye comfort index
4. Evaluation of ocular signs and symptoms
5. Integrity of ocular surface
 - a. Includes stains

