- Evaluation of variables: The data of the evaluation of the variables listed below can be taken from the scrutiny visit, as long as it does not exceed 7 days prior to this visit. It is the IP's prerogative to decide whether to use the information from the screening visit or to repeat the evaluations on this visit.
 - Intraocular pressure
 - Visual capacity
 - TRL
 - Integrity of ocular surface
 - Eye symptoms
 - Subsequent segment
 - vital sign
- Eye comfort index: see 6.4.3.2 Eye comfort index
- Delivery of the subject's diary: It refers to the delivery by the IP to the subject, the subject's daily instrument.
- Adverse events: see 6.4.3.4 Presence of adverse events

6.5.1.3 *Visita 1*

- Evaluation of adherence: refers to the assessment made by the IP according to section 6.3.2.1 Procedure to monitor adherence
- Adverse events: see 6.4.3.4 Presence of adverse events
- Intraocular pressure: see 6.4.3.5 Intraocular pressure
- Visual ability: see 6.4.3.1 Visual capacity
- TRL: see 6.4.3.9 Rupture time of the tear film
- Integrity of ocular surface: see 6.4.3.3 Integrity of ocular surface:
- Eye symptoms: 6.4.3.8 Ocular symptomatology
- Vital signs: see 6.4.3.7 Vital signs
- Submission of the subject's diary: see 6.5.1.2 Baseline visit
- Return / daily evaluation of the subject: refers to the delivery of the subject's diary to the IP by the subject. The PI will review the diary to assess its correct filler, evaluate postinstillation symptoms and record applications.
- Continuity assessment of the subject: refers to the determination by the IP and desire of the subject to continue with their participation in the study.

6.5.1.4 *Final Visit*

- Laboratory sample taking: ver6.4.3.11 Laboratory tests
- Pregnancy test: see 6.4.3.10 Pregnancy test
- Return of intervention: see 6.5.1.3 Visit 1.
- Evaluation of adherence: refers to the assessment made by the IP according to section 6.3.2.1 Procedure to monitor adherence
- Adverse events: see 6.4.3.4 Presence of adverse events
- Intraocular pressure: see 6.4.3.5 Intraocular pressure
- Visual ability: see 6.4.3.1 Visual capacity
- TRL: see 6.4.3.9 Rupture time of the tear film
- Integrity of ocular surface: see 6.4.3.3 Integrity of ocular surface:
- Eye symptoms: 6.4.3.8 Ocular symptomatology
- Subsequent segment: see 6.4.3.6 Subsequent segment
- Vital signs: see 6.4.3.7 Vital signs
- Eye comfort index: see 6.4.3.2 Eye comfort index
- Return / daily evaluation of the subject: see 6.5.1.3 Visit 1.

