Those subjects who comply with an adherence greater than 60% will be included in the statistical analysis to meet the objective of the study. It was considered that from the minimum dose necessary to obtain a pharmacological effect and the presence of adverse events (exposure) is sufficient to fulfill the general objective of the design, according to the pharmacological characteristics of the product under investigation.

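### The set labelled intention-to-treat is final-visit completers, with a further adherence filter above 60%, so a subject who stops for intolerance can drop out of every primary comparison except adverse-event reporting

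*Combined protocol and SAP*

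**What the plan says.** Section 8.3.3 covers the analysis population and, by its title, missing data. Its whole content is: "An intention-to-treat analysis will be carried out, where the data of the participants who have completed the final visit will be included". It gives no method for missing data.

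Section 8.3.1 ends with a second condition: "Those subjects who comply with an adherence greater than 60% will be included in the statistical analysis". It does not say which adherence measure is meant. Section 6.3.2.1 uses the diary to decide whether a subject continues. Section 6.3.2.2 says: "The final adhesion will be determined by the sponsor by means of the weight of the bottle".

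Section 6.2.3 lists the grounds for elimination. They include a serious adverse event, "No tolerability or hypersensitivity to any of the investigational drugs", and "Adherence <50% determined by the diary of the subject, of the established dose of the pharmacological intervention in any of the visits". It does not say whether an eliminated subject attends later visits or what happens to the data already collected.

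Section 6.4.4 sets the final visit on day 8, with days 9 and 10 allowed, and adds: "Not before, since the application of the medication will not be completed as dictated the protocol". The schedule has no early-termination visit. Visit 1 (day 3) includes a continuity assessment, the "determination by the IP and desire of the subject to continue with their participation in the study" (6.5.1.3). After a missed appointment, Section 8.1.1 has the centre try for a new one inside the window or an unscheduled one. Failing that, the minimum data are adverse events and the reason for leaving.

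One outcome has a wider set. For adverse-event reporting, Section 8.3.1 says "all eyes of those participants who were randomly assigned to an intervention group after the baseline visit will be considered".

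**The concern.** Tolerability is a primary outcome, and failing to tolerate the drug is a ground for elimination. With a completer rule on top, the outcome can decide who is analysed. The subjects most informative about burning, foreign body sensation, itching, hyperemia or staining are the likeliest to stop, and so the likeliest to be missing from those comparisons.

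The intention-to-treat label hides this, because a reader will take it to mean that everyone randomised is counted. The set matters twice over: it feeds the descriptions of tolerability promised in Section 5.5.2, and it feeds the rule in Section 8.3.1 that declares the product safe and tolerable when no primary variable differs.

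**Working it through.** The plan gives no figure for how many subjects these rules would remove, so there is none to reproduce.

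**Inputs.** 15 subjects per arm (6.6). Summary schedule: 8 applications a day on days 1-2 and 4 a day on days 3-7, so 2×8 + 5×4 = 36 per eye. Sections 6.3.1.1 and 6.3.1.2 give 8 a day with no step-down; over 7 days that is 56. Alpha 0.05 (8.3.1). Reaction rates of about 1-3% for the most frequent reactions, and 0.63% with any reaction in the phase IV study (5.3.1.4).

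**Step 1: the two filters applied to a subject who stops early.** Adherence = applications made / applications indicated for the full course.

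| Takes every drop, then stops | Summary schedule | Section 6.3.1 wording | Above 60%? |
|---|---|---|---|
| after day 3 | 20/36 = 55.6% | 24/56 = 42.9% | no on both |
| after day 4 | 24/36 = 66.7% | 32/56 = 57.1% | yes / no |

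Bottle weight gives the same ratio if each application removes one nominal drop weight: for both eyes, 40/72 = 55.6%.

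The subject who stops after day 3 fails the adherence filter even if the final visit is completed. The subject who stops after day 4 passes it on the Summary schedule, but falls outside Section 8.3.3 without a visit on days 8 to 10. An unscheduled appointment before day 8 does not help, because it is not the final visit. The second row also shows that the two dosing statements give different answers on inclusion.

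**Step 2: what is lost.** Intraocular pressure, visual capacity, staining, hyperemia, chemosis, burning, foreign body sensation and itching are all measured at Visit 1. For a subject who leaves after that visit these values exist, but the subject is outside the set. The comfort index and laboratory tests have no Visit 1 value, so nothing can be recovered for them.

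**Step 3: effect on a test (illustration).** Assume a symptom scored present or absent, intolerance at rate q in the PRO-174 arm and 0 in the comparator, and background symptom rate b in both arms. Every intolerant subject has the symptom, and none returns for the final visit.

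- All kept: Bin(15, q + (1−q)b) against Bin(15, b).
- Completers only: Bin(n, b) against Bin(15, b), with n = 15 − Bin(15, q).

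Summing the exact probabilities of all tables with uncorrected Pearson p ≤ 0.05 gives these rejection rates:

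| q | b = 10%: all kept | completers | b = 40%: all kept | completers |
|---|---|---|---|---|
| 1% | 2.7% | 2.5% | 4.9% | 5.0% |
| 3% | 3.4% | 2.5% | 4.9% | 5.2% |
| 7.3% | 6.2% | 2.8% | 5.4% | 5.4% |

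The 7.3% is the adverse-event percentage in Section 6.6.1, which that section attributes to a different preparation. It is only an upper reference point.

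In counts, the smallest split against zero that reaches Pearson significance is 4/15 v 0/15: χ² = 30×(4×15)²/(15×15×4×26) = 4.62, p = 0.032 (Fisher p = 0.10). Among completers it becomes 0/11 v 0/15. With 3/15 v 0/15, p = 0.068. The chance of two or more intolerant subjects among 15 is 1 − (1−q)^15 − 15q(1−q)^14, which is 1% at q = 1% and 7% at q = 3%.

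**The case against.** The strongest reply has four parts.

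*The rules do not contradict each other.* The 50% diary rule governs staying in the study; the 60% and final-visit rules govern analysis. All three can apply together. This stands: the fault is that the filters select on the outcome and their combination and measure are unstated. The measure is also less open than it may look, since Section 6.3.2.2 points to bottle weight for final adherence, though Section 8.3.1 does not say so.

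*Exclusion is conditional.* A reader might infer that every eliminated subject disappears from the analysis. The documents do not support that. Nothing bars an eliminated subject from attending on days 8 to 10, and one who does meets Section 8.3.3. It is only partly reassuring, because Step 1 shows that such a subject can still fail the adherence filter.

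*Adverse-event reporting keeps everyone randomised.* This is a real safeguard. A reader might infer that the completer rule yields a false safe-and-tolerable verdict. That does not follow: the verdict requires no difference in any primary variable, adverse events are one of them, and intolerance recorded as an adverse event stays in that comparison. How adverse events will be tested is a separate question.

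*The numerical effect is small at the cited rates.* This stands too. At 1-3% the change is under one percentage point, and with a 40% background it runs slightly the other way, so a general claim of bias toward no difference is not established. The model is also crude: symptoms are graded in five levels, and no intolerance rate is given. Counting eyes would make the effect look larger only by counting each subject twice, and a much higher intolerance rate would have no source in the documents.

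**Conclusion.** The point holds and should be fixed. As written, the intention-to-treat analysis is a completer analysis with an adherence filter. A subject who stops for intolerance is left out of every primary comparison except adverse-event reporting if either the final visit is missed or full-course adherence is 60% or less.

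The effect on tests is small: 0.2 to 0.9 percentage points at 1-3% intolerance with a 10% background (2.7 v 2.5 and 3.4 v 2.5), and 0.1 to 0.3 points in the other direction with a 40% background. This rests on the assumptions in Step 3, and the cited percentages are reaction rates, not elimination rates.

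The firmer consequence needs no rate. Visit 1 measurements already taken from the subjects who tolerate the drug worst go unused, in a trial of 30 subjects whose stated objectives are descriptive.

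The adherence result assumes that the 60% refers to the full course. The day-3 case fails on both dosing statements; the day-4 case depends on which one applies.

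**What to change.** Reword Sections 8.3.1 and 8.3.3 as follows.

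1. Keep adverse-event reporting on all randomised participants, as now. Do not narrow it to treated subjects.
2. For the other primary variables, analyse as allocated all randomised subjects who received at least one drop and have any post-baseline value, by visit. Visit 1 comparisons use everyone with Visit 1 data. Final-visit comparisons use everyone with final-visit data, whatever their adherence. For symptoms and signs, also report the worst post-baseline grade, so that subjects with Visit 1 data only are counted. The comfort index and laboratory tests stay on observed final data.
3. Tabulate and compare, by arm and on all randomised subjects, discontinuations and eliminations for intolerance, hypersensitivity or a serious adverse event. Section 8.1.1 already asks for the reason for leaving when a missed visit cannot be rescheduled.
4. Keep final visit completed plus adherence above 60% as a per-protocol sensitivity set. Name its adherence measure and remove the intention-to-treat label from it.

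The dosing statements in the Summary and in Sections 6.3.1.1 and 6.3.1.2 must be reconciled, because they set the adherence denominator. Treatment-stopping criteria are unchanged.

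The cost is wording, one table and one sensitivity analysis, with no new visit. Subjects with no post-baseline value will count only in the adverse-event and discontinuation comparisons, and missing comfort-index and laboratory values stay missing.
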